### Study Procedure

The research program for this R34 Exploratory Research Award will be divided into three phases. **Phase I** (the development phase) will consist of manual development, focus groups, and the open trial. During this phase, we will develop our computer based intervention, SHE, which will be informed by focus groups. We will also conduct a nonrandomized trial with 15 women (open trial) to gain experience with the screening, assessment and intervention, which will inform subsequent refinement of protocol and procedures following the guidelines for Stage I treatment development. The proposed study will use a sophisticated intervention development tool, CIAS developed by [name], that has been successfully used with perinatal substance using women. The Co-I ([name]) has been trained by [name] to use this software and successfully developed and tested an intervention to reduce alcohol use in an urban setting, for high-risk pregnant women. During **Phase II** (the pilot study phase), we will conduct a **two-group, randomized controlled study** with a sample of 60

women endorsing inclusion criteria (see Section C.2.3). Study participants will be randomly assigned to either the SHE or a time-and-attention-matched control condition to assess the feasibility of the research design, the acceptability of SHE, and to provide some preliminary information about the direction of intervention effects for substance using days over a 6-month post-shelter period (primary outcome) and total days of substance use services received and IPV severity over a 6-month post-shelter period (secondary outcomes). During **Phase III (Revision Phase)**, the team (i.e., Drs. [name], [name], [name],

[figure not shown]

Figure 1 Flow of Intervention

and [name]) will review experiences and outcomes for both the open trial and the pilot study. Results from this proposal will be used as preliminary data for a fully-powered, larger clinical trial.

The SHE Program will consist of a 50 minute intervention on the Tablet PC. There will be a 15-minute “booster” session on the Tablet PC within 3 weeks after the 50 minute intervention session to reinforce the effects of the intervention. Both sessions will take place in a private shelter setting while the participant is a resident of the shelter. The SHE Program will follow the guidelines for brief interventions and contain the recommended elements for brief interventions: feedback of risk that is personalized (F), emphasis on personal responsibility (R), non-confrontational advice to change (A), a menu of change options (M), empathy as a counseling style (E), and enhancement of self-efficacy (S)—or FRAMES. Motivational strategies such as reflective listening and tailored summaries and feedback will be utilized to enhance participants’ motivation.

Some aspects of MI (and FRAMES model) are difficult to translate *literally* into a computer-based intervention (e.g., empathy). The software relies heavily on realistic interactions with a three-dimensional animated narrator to mimic a non-judgmental, empathic, and non-threatening demeanor of a person-delivered brief, motivational interventions. The narrator reads each item for the participant, and guides her throughout the process using reflections and self-deprecating humor. Throughout the development phase of the study, we will receive feedback on participants’ sense of autonomy, of being supported and reinforced in their decisions, and on the tone of the module. The software, including the three-dimensional animated narrator, has been found in previous research to be well-understood and well-liked by low-income women.

The computerized intervention will begin with a baseline **assessment** of substance use. Participants will then receive immediate “profiles” (**personalized feedback**) based on their answers to assessments. A substance use profile will summarize their typical pattern of substance use, their substance use risk level, the known health and societal consequences associated with their level of substance use, and the negative consequences they identified as resulting from substance use. Next there will be an **education** component that will deliver facts about the woman’s substance use, and associated risks for the woman, including partner substance use; the **bidirectional relationship** between substance use and IPV; and risks of untreated substance use such as increased risk of IPV.

A limitation of some clinical trials of MI-based interventions for substance use and most clinical trials of behavioral interventions for IPV is the imbalance in intensity of sessions between the experimental intervention and control group, which makes it difficult to determine if intervention differences are attributable to differences in attention between the conditions or to the “active ingredients” of the intervention. Because the proposed non-MI control condition will be matched for duration, level of interactivity, and mode of delivery and has been shown to be a credible control condition, it will provide a reasonable test of the effect of the SHE Program. Furthermore, our control condition will have no overlapping content with the SHE Program. Finally, since both conditions will be computer-based of similar duration, the blinding of research staff to experimental condition will be facilitated.

There are no standard or universal procedures in place for screening and brief interventions for women with IPV and substance use issues. Like most battered women shelters, WCRI does not conduct any formal or systematic substance use-related assessments or interventions for their residents, besides appropriate referrals for substance use treatment, if requested, or if needed (i.e., resident discloses difficulties or is found to be using alcohol or drug during her shelter stay). All participants who consent for the RCT study (and open trial) will receive a list of appropriate substance use treatment referrals and community resources (e.g., NA, AA) and a brochure on alcohol and drug risks.

The intervention will be tailored on the current substance use status of each participant (see Figure 1). Computer software can easily deliver such a bifurcated treatment approach –

such an intervention design is consistent with evidence that motivational approaches may work best with less motivated individuals. The intervention will contain language referring to either substance use in general (past or present behaviors and beliefs) or current substance use, and will not assume current substance use. For women who state that they have already quit (see “No” in Figure 1), the three-dimensional animated narrator will present a section that will focus on how they can remain abstinent now and after they leave the shelter (Relapse Prevention). An example in this section will include if the woman decides to return to her abuser, how avoiding using with her abuser could decrease her risk for abuse and for subsequent substance use. These women (i.e., those who have already quit) will have the option to create a personalized **Safety Plan**, and can select from a menu of potential personal change goals (i.e., maintain their change) and/or optionally, they can enter their own change goals in free text.

Women who endorse current substance use will be asked about their interest/readiness in quitting their substance use (“Ready to Quit?”) leading to a bifurcated treatment response such that those participants reporting a goal of immediate abstinence will move more quickly to a section consistent with primary goal-setting for substance use reduction. This arm will follow closely the guidelines established in previous intervention studies which will include components of a quit contract and will assist the woman in identifying specific goals and a timeline for reaching these goals. These participants will have the option to create a personalized **Safety Plan** that will include the specific goals that the women have identified and/or optionally, can enter their own change goals in free text. Some example of goals will include attending AA or NA, attending substance use treatment, speaking to shelter staff about coordinating substance use treatment, planning for support groups after leaving the shelter such as IPV support groups. For the remaining participants who report not being ready to quit at this time, the narrator will present sections including **pros and cons, feedback, and optional goal-setting**. Specifically, in the pros and cons section, the narrator will normalize feelings of ambivalence about substance use, noting that most people can identify sides to their use that are both positive and negative. For example, the narrator will first ask for the good things about substance use and provide a checklist in which the participant endorses as many pros as they would like. The narrator then notes that for many people there are also some “not so good” aspects to substance use, and presents another checklist in which the participant endorses as many cons of substance use as they would like. Then the narrator reflects back to them the specific pros and cons that they selected and notes that feeling two ways about one’s substance use is quite normal. For example, the narrator would say, “You really seem to feel two ways about this. On the one hand, you like the way that smoking marijuana helps you relax when you have reminders of the abuse. But at the same time, it is only a temporary fix for your problems.” In the feedback section, the narrator will first present participants with normative feedback regarding their typical substance use using an easy-to-read graphical display and clear description of what the feedback means. This feedback includes key pieces of information: how much the participant reported using, how much they think most other women use, and how much of it other women actually use. Normative feedback is followed by feedback with the specific negative consequences that the participants reported having experienced as a result of their substance use. The narrator will then elicit brief elaborations of negative consequences using simple questions keyed to each type of consequences. For example, if a woman endorsed the item regarding health problems as a result of substance use, the narrator could ask, “What sorts of health problems have you had?” and provide a checklist of possible response. A follow up question could then ask the participant to choose ways in which their health could be improved if they did decide to make a change. There will be a section that will provide feedback on each participant’s self-reported readiness to change with regard to substance use. In the optional goal-setting section, the narrator will begin by briefly summarizing the state of each participant’s ambivalence regarding her substance use, and the factors pulling her in either direction. The narrator then asks if she would like to set a change goal. If she does not wish to do so, the narrator reflects her lack of readiness at this time and elicits information

regarding what signs would tell the participant that she did need to change. If the participant does wish to set a change goal, the program will guide her through a brief change plan process. In this process, the participant will be asked when, why, and how she would like to make a change regarding her substance use and be given the option to create a personalized **Safety Plan** that incorporates the changes the woman has identified and/or any other changes she would like to add in free text. All SHE participants will be provided with an optional one-page print-out of the Safety Plan as a resource.

**Booster session:** Within three weeks of the intervention, women will complete a 15 minute computerized **booster session** in which they will review the relevant components of the intervention session for each woman (e.g., pros and cons, feedback, and goal-setting) and their own **personalized safety plan**. The booster session will bolster the effects of the intervention. Women will be given the option to revise their personalized **Safety Plan**, and can select from a menu of potential personal change goals; they can enter their own change goals in free text. All participants will be provided with an optional one-page print-out of the Safety Plan as a resource.

[figure not shown]
### Methods - Open-Pilot Trial

In Month 7, we will begin recruitment for the nonrandomized trial with 15 women to gain experience with the screening, assessment and intervention, and to inform subsequent refinement of protocol and procedures. After the baseline assessments have been completed, the study participant will complete the SHE Program (an initial session plus booster session within three weeks prior to leaving the shelter) and complete 3- and 6-month follow-up assessments. After the completion of the SHE Program, participants will complete a computer based intervention specific End-of-Intervention Questionnaire, which will address participants' perceptions of the helpfulness of each intervention component, including timing and length of the sessions and their level of comfort with research procedures. Participants will discuss their responses at an end-of-intervention exit interview with [name] or a trained research assistant to aid in intervention revisions.

### Methods - Randomized Pilot Trial

Women who are residents of a battered women's shelter (the Women's Center of Rhode Island [WCRI], Sojourner House, New Hope, or Battered Women's Shelter of Summit and Medina Counties), who are at risk substance users within the 3 months prior to entering the shelter as determined by the screener, the NIDA-Modified ASSIST, and endorse IPV within the 3 months prior to entering the shelter as determined by the screener, the WAST (Phase A) will be eligible for the RCT (Phase B). Phase B will use a two-group, randomized, controlled design with 60 shelter residents. After eligible participants consent to participating in the RCT and complete the computer-based baseline assessments the (computer) narrator will "flip a coin" and randomly assign participants to the SHE Program (an initial session plus booster session within three weeks after the initial session) or to the time and attention matched control condition (an initial session plus a booster session within three weeks after the initial session; both consisting of video viewing of popular shows and preference ratings). Next study participants will complete their assigned computer-based intervention. There will be 3- and 6-month post-shelter computer-based follow up assessments (see figure 2 below).

**Figure 2: Methods for Phase B**

For those who have completed Phase A (i.e., the screener) and who are eligible (i.e., endorse at risk substance use and IPV in the three months prior to shelter stay), research staff will inform them about the clinical trial, explain the informed consent process, and explain the study procedures. Refusal rates will be recorded and residents who refuse participation will be asked to provide their reasons for refusal. Women who provide informed consent will be given the computer again, and complete an approximately 20-30-minute baseline assessment using the ACASI software. The informed consent process, the computer-based baseline assessments, and computer-based sessions for both conditions will be conducted in a private space at the shelter. Follow-up assessments will be conducted in a private room or at a location that is a convenient location for the woman and one that will provide a confidential, safe, and comfortable environment for the participant. If a follow-up assessment is being conducted at a woman's home, the research team may ask her if she will allow the research team to use her internet connection to run the computer program on the Tablet PC. If a participant does not have internet access or does not allow the researchers to access her internet connection, the research team will use our own portable air card for wireless internet connection. Participants will be reminded that if they do not wish to use their internet connection, they can still participate in the study. All participants in this study will receive care as usual from shelter staff; no screening, referral, or counseling will be withheld in any way at any time.

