IPV: The Composite Abuse Scale (CAS) is a widely used self-report of behaviors scale with 4 subscales that measure severe, combined abuse, emotional abuse, physical abuse, and harassment. The CAS has recently been published in the Centers for Disease Control and Prevention compendium of intimate partner violence measures. It consists of 30 items presented in a six point format requiring respondents to answer “never”, “only once”, “several times”, “monthly”, “weekly” or “daily” in a twelve month period.

The Cyber Stalking Scale measure is a 6 –item measure and assesses the use of technologies in stalking and harassment.

Safety Behavior Checklist (SBC) has 15 items that assess the use of strategies suggested to keep victim safe (e.g., hiding money and extra clothing).

*Theorized Mediators: The Confidence Ladder* will be used to assess the participants’ levels of confidence regarding their ability (self-efficacy) to change and abstain from substances. *Readiness Ruler* will be used to assess the degree to which participants’ are ready to cut down or quit alcohol or drugs.

Women who participated in the SHE intervention will complete a computer-based measure at the 3- and 6-month follow-up assessment to determine the extent to which participants achieved their goals on their personalized plan; an indication of the degree to which the SHE intervention had an impact on behavioral change. This measure will follow a similar format to the Effectiveness in Obtaining Resources Scale, which assesses battered women’s effectiveness in obtaining various resources.

At follow up, if a participant is unable to meet in-person to complete the assessments (e.g. participant has moved out of state), she will be given the option of participating in the assessment over the phone. Phone sessions will consist of the research assistant administering all the follow up assessments listed above via a phone session, with the exception of breathalyzer, urine, and hair sample testing.

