The use of computer technology for gathering self-report data further enhances overall protection. Data will be encrypted in transit between user and server. Importantly, no identifying information will be entered into the ACASI. Given the sensitive nature of this research, the computer software will simply generate a code number for each participant. Additionally, all forms with participant information will be marked with a code number and not with the participants' name. The PI will keep the link between the participant code number and name under lock-and-key. Any information about a participant will never be released to outsiders without their explicit consent, except in the event of abuse of children/elderly/handicapped (report to the State of Rhode Island) or a medical emergency, when pertinent medical information will be given to the medical personnel caring for the individual.

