Details of the research are not provided to anyone other than the actual participant. During each contact, participants will first be asked if it is a safe time to speak. Safe contact for follow-up assessments will be negotiated at each stage of the research. Both written and verbal contacts will be vague and never mention that the research involves partner violence. Follow-up interviews will be scheduled at a safe location. Safety plans will be negotiated up front (e.g., code words, cover story for reason for interview) if ever the abuser were to interrupt a phone call or assessment. Any handouts with important information (e.g., hotline numbers) will be available in wallet size copies without any reference to the study or name of organization. Participants' safety contact information will be updated monthly to determine if the contact information they previously provided is still accurate and safe. Participants will be given contact information for the research team and asked to let us know if the contact information they provided is no longer safe. All research personnel (i.e., interventionist, research assistant) will be able to call the PI for advice on any case where there is a concern for the safety of the respondent and the PI will be available at all times by pager.

Although the proposed intervention seeks to help a woman to develop strategies for keeping herself safe, it is possible that a woman who participates in the study might be at increased risk of partner violence because of increased assertiveness. At each follow-up assessment, our assessment of community resource use will ask about participants' visits to emergency rooms, health professionals, etc. The Composite Abuse Scale (CAS) will be administered to monitor abusive experiences in the context of a woman's relationship since the last assessment. Women will be asked at follow up assessments (3- and 6-month) about any occurrences of hospitalizations for medical, psychiatric, or substance use issues or emergency room visits, and whether or not any of these events were related to IPV in order to better gather information regarding any potential serious adverse events. These events will be reported to the Data Safety Monitoring Board (DSMB).

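### At home follow-ups the woman's own internet connection comes before the study's air card, and the partner-violence safeguards do not cover the home network

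*Protocol*

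**What the plan says.** Under Figure 2: Methods for Phase B, the protocol allows follow-up assessments at home. In that case "the research team may ask her if she will allow the research team to use her internet connection to run the computer program". Where she has no access or does not agree, "the research team will use our own portable air card for wireless internet connection". The same paragraph adds: "Participants will be reminded that if they do not wish to use their internet connection, they can still participate in the study". It also asks for a follow-up place that is convenient and "one that will provide a confidential, safe, and comfortable environment for the participant".

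The section Protection against risk repeats the location rule: "Follow-up interviews will be scheduled at a safe location". Adequacy of protection against risks states: "Data will be encrypted in transit between user and server". It adds that participants are known to the software only by a code number. The SAP does not deal with this matter.

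**The concern.** The participants have recently left, or are leaving, abusive partners, and the protocol accepts that some will go back or stay in touch. Both Potential risks and Protection against risk say that a woman in that position may face more abuse if the partner learns that she is in the study. The protocol therefore limits the traces the study leaves in her life. The home internet connection is a further channel that could leave one, and the partner may share it or have set it up. At a home visit, staff may turn to that channel first, although the study plans to have its own connection available. What is at stake is participant safety and confidentiality. If harm followed, it would be partner violence brought about by study participation.

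**Working it through.** No arithmetic applies, and the documents give no figure to reproduce. The check sets the home-visit procedure beside the protocol's own safety provisions.

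1. **Order of the two connections.** Figure 2: Methods for Phase B puts the woman's connection first, by request and with her agreement. The air card comes second, if she has no internet or does not agree. No reason is given for this order.

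2. **Recognised risk.** Potential risks and Protection against risk both name discovery by the abuser as a hazard for women who are still in contact with him or her.

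3. **Channels that are covered.** Protection against risk provides a research phone line with a blocked number, deliberately vague spoken and written contacts, and wallet-size handouts that do not name the study. It also plans code words or a cover story in case the abuser interrupts a call or an assessment, and states: "Details of the research are not provided to anyone other than the actual participant". Retention describes a generic Facebook page that reveals nothing about the study. The protocol thus already treats communication traces as something to control, and it foresees that an abuser could be near a follow-up.

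4. **Channel that is not covered.** None of these provisions mentions the home network, who controls it, or what a visit might leave on it. The text available does not say that the woman is told of this when she is asked. Consent pages were removed from the documents, so nothing can be said about what they contain.

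5. **What the existing safeguards leave open.** Encryption and the absence of identifiers protect the answers. The safe-location rule protects the setting. Her freedom to decline protects women who already know that the network is unsafe. What is left is the possibility that someone with access to the network could see that an unfamiliar device joined it, when, and perhaps which service it contacted. This is general technical reasoning, not a fact in the documents.

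6. **Is partner monitoring documented?** Measures includes a Cyber Stalking Scale that "assesses the use of technologies in stalking and harassment". This shows that the investigators consider technology-based abuse relevant to these women. It is an outcome measure and says nothing about home networks.

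7. **Number of visits affected.** The share of follow-ups held at home is not stated. Measures also lets a woman who cannot meet in person be assessed by phone. No usable count follows from the documents.

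**The case against.** The strongest reply is that the protocol only permits the request. Staff may ask, she may refuse, and she is reminded that refusal does not end her participation. She is also well placed to know who shares her network. A home visit should take place only after the location has been judged safe. Someone watching the home could more readily notice a staff visit with a breath test, a urine cup and hair sampling than a network log entry. All of this stands, and it keeps the point small. It does not close the gap. The reminder concerns participation rather than network traces, and the arrangement leaves a technical security judgement to the woman when the study has an alternative of its own.

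A second reply concerns the remedy. If the woman's connection were ruled out altogether, visits without air-card signal would move to paper and lose computer self-report, which the protocol prefers because it helps disclosure. This also stands, and the fix keeps her connection as a guarded second option.

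A reader might infer three stronger things that the documents do not support:

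- **That the procedure contradicts the confidentiality rules.** Those rules concern what other people are told, how contacts are worded and what handouts show. An encrypted session without identifiers breaks none of them. The home network is an omission, not a contradiction.
- **That an abuser is known to control or inspect the connection.** No section says so.
- **That every follow-up is exposed.** Two follow-ups for each of 60 randomised women gives 60 × 2 = 120 visits, but that assumes full retention and every visit in person at home. Data Analysis expects complete data on only about 41 women. Adding 15 × 2 = 30 open-trial visits assumes that the home-internet procedure applies there, although it is described only for the randomised trial.

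**Conclusion.** The point holds in a limited form. The protocol lets staff turn first to the woman's own connection at home visits and keeps the study's air card as the fallback. Its partner-violence safeguards, otherwise detailed, do not extend to the home network. The remaining exposure is at most a record that a device connected, not the content of her answers. Its frequency is unknown because the number of home visits is not given.

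The conclusion rests on two assumptions from outside the documents: that an abuser may share or monitor the network, and that a connection can leave a visible trace despite encryption. Both are plausible in this population, and a precaution does not need proof of actual monitoring. Sample size, outcomes and analyses are unaffected. The point is a cheap improvement to participant safety, not a flaw in the trial's inference.

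**What to change.** Reverse the order in Figure 2: Methods for Phase B:

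- At home follow-ups, use the study's air card first.
- Use the woman's connection only if the air card has no signal, and only after staff have asked whether anyone else controls or can monitor that network and she then agrees.
- Otherwise use the paper copies that Measures already allows for technical problems.

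A matching line in Protection against risk would bring the home network under the same safeguards as calls, contacts and handouts. The cost is mobile data, a short protocol edit, one extra question where there is no signal, and occasional paper completion with some loss of computer self-report.
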